## 3. Population Analysis Set

### 3.1 Full Analysis Set

The Full Analysis Set (FAS) will consist of all enrolled Patients who received at least one dose of Acabrutinib.

Document Title:	Document ID:	BP04-01
Statistical Analysis Plan	Version Number:	3.1
	Effective Date:	25-Nov-2021

The FAS will be used for all analyses of safety and efficacy.

#### 4. Sample Size and Power Calculations

The primary endpoint of the trial is to demonstrate the safety profile of Acalabrutinib in routine clinical practice as assessed by the incidence of adverse events (AEs) (Serious and Non-serious AEs) observed during the trial. As per the Health Authority requirement, the total sample size of the study will be approximately 100.

#### 5. Patient Characteristics and Study Conduct Summaries

##### 5.1 General Considerations

Statistical Analysis will be performed using SAS (version 9.4 or higher) software (SAS Institute Inc USA). Categorical variables will be summarized with the frequency and percentage of Patients in each category. Continuous variables will be summarized descriptively with the number of Patients, mean, standard deviation, minimum, median and maximum values.

##### 5.2 Decimal Point

Unless otherwise noted, means, median, will be presented to one decimal place more than the measured value, the same decimal as the measured value, percentages and confidence intervals will be presented to two decimal places and p-value will be presented to three decimal place. Percentages after zero counts will not be displayed and percentages equating to 100% will be presented as 100%, without any decimal places.

##### 5.3 Disposition of Patients

Patient disposition table will be based on all enrolled Patients who consented to participate in the study. The following summaries will be included in the disposition table: total number of Patients screened in the study, number and percentage of Patients who failed screening, number and percentage of Patients who completed the study, and number and percentage of Patients who discontinued from the study with reason for discontinuation.

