4.1.4 Follow-Up Phase (End-Of-Study)

The Follow-up Phase will begin once a patient discontinues study drug or completes the Treatment Phase. The follow-up phase will continue until 28 days after last dose, loss to follow up, withdrawal of consent for study participation, or end of the study, whichever occurs earlier. A follow-up will be conducted 28 days after the EOT visit via a phone call. This will be considered as End-of-Study Visit. Every effort should be made to conduct the End-of-Study Visit.

Patients who are observed to receive clinical benefit from Acalabrutinib after completion of treatment phase, may continue to receive Acalabrutinib, if in the opinion of their treating physician they are continuing to derive clinical benefit from continued treatment or have not progressed clinically. The details on “Post-Trial Access” are provided in section 1.2.

For details on treatments given during the study, refer Section 6.1 Treatments Administered.

For details on what is included in the efficacy and safety endpoints, refer Section 3 and 8.

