4.4 End of study definition

The end of the study is defined as the last expected visit/contact of the last patient undergoing the study.

A patient is considered to have completed the study when he/she has completed his/her last scheduled visit or last scheduled procedure shown in the SoA

Refer Appendix A 6 for guidelines for the dissemination of study results.

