7. DISCONTINUATION OF STUDY DRUG

7.1 Discontinuation of study treatment

Patients may be discontinued from the investigational product in the following situations:

- Patient decision. The patient is at any time free to discontinue treatment without prejudice to further treatment.
- Adverse Event that in the opinion of the Investigator or the Sponsor contraindicates further dosing
- Severe non-compliance to study protocol that, in the opinion of the Investigator or Sponsor, warrants withdrawal, e.g., refusal to adhere to scheduled visits etc.
- Any AE that meets criteria for discontinuation, as defined in Appendix D
- Initiation of alternative anticancer therapy including another investigational agent
- Disease progression as per the Investigator's clinical and imaging assessment.
- Pregnancy or intent to become pregnant.

If the patient is discontinued from the study, the patient will be followed up until the start of subsequent anti-cancer intervention or up to a duration of 28 days, whichever is earlier.

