## 6. Efficacy Analysis Strategy

### 6.1 Efficacy Endpoints

#### 6.1.1 Primary Endpoint

- Adverse Events (AEs), Serious Adverse Events (SAEs), and AEs of Special Interest (AESI) including Arrhythmias (Atrial Fibrillation), Anaemia, Hypertension, Bleeding, Infections, Reasons for discontinuation and second primary malignancies

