## 8. Mock Tables

Table 14.1.1. Patient Disposition in the Study

	CLL/SLL (N=xx)	MCL (N=xx)	Total (N=xx)
	n (%)	n (%)	n (%)
Patients Screened	xx (xx.xx)	xx (xx.xx)	xx (xx.xx)
Screen Failures	xx (xx.xx)	xx (xx.xx)	xx (xx.xx)
Patients Completed the study	xx (xx.xx)	xx (xx.xx)	xx (xx.xx)
Patients Discontinued the study	xx (xx.xx)	xx (xx.xx)	xx (xx.xx)
Reason for Discontinuation			
Patient Decision	xx (xx.xx)	xx (xx.xx)	xx (xx.xx)
Adverse Event	xx (xx.xx)	xx (xx.xx)	xx (xx.xx)
Severe non-compliance to study protocol	xx (xx.xx)	xx (xx.xx)	xx (xx.xx)
Initiation of alternative anticancer therapy including another investigational agent	xx (xx.xx)	xx (xx.xx)	xx (xx.xx)
Disease progression	xx (xx.xx)	xx (xx.xx)	xx (xx.xx)
Pregnancy or intent to become pregnant	xx (xx.xx)	xx (xx.xx)	xx (xx.xx)
Other	xx (xx.xx)	xx (xx.xx)	xx (xx.xx)
Other 1	xx (xx.xx)	xx (xx.xx)	xx (xx.xx)
Other 2	xx (xx.xx)	xx (xx.xx)	xx (xx.xx)

- The Capital "N" in the column header represents the total number of all Enrolled Patients.
- The small "n" in summary statistics represents the total number of Patients.
- Percentages in the "Patients Screened", "Screen Failures", "Patient completed the study" and "Patients Discontinued the study" rows are based on the number of Patient in each group.
- Percentages in the "Reasons for Discontinuation" rows are based on the number of Patients Discontinued study in each group.
- Note: Screened Patients are those who signed the informed consent
- Source :Listing 16.2.1.1, listing 16.2.1.2

Document Title:	Document ID:	BP04-01
Statistical Analysis Plan	Version Number:	3.1
	Effective Date:	25-Nov-2021

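### Reasons for discontinuation, a listed primary outcome, are tabulated only for patients who leave the study, so early stops of acalabrutinib may be under-counted or counted under two definitions

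*SAP*

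**What the plan says.** **Outcome.** The SAP's primary endpoint list (6.1.1) ends with "Infections, Reasons for discontinuation and second primary malignancies", and protocol Table 2 has the same item. Neither says whether drug or study discontinuation is meant. SAP 6.3.1, which sets out the primary analysis, does not mention the item.

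**Planned output.** SAP 5.3 gives the "number and percentage of Patients who completed the study, and number and percentage of Patients who discontinued from the study with reason for discontinuation". Mock Table 14.1.1 puts the reasons under the row "Patients Discontinued the study" and bases their percentages on that group. Listing 16.2.1.2 has one completion field, one date and one reason for withdrawal.

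**Protocol.** Section 7.1 introduces its list of reasons with "Patients may be discontinued from the investigational product in the following situations"; leaving the study is dealt with separately, in 7.2. Section 4.1.4 states: "The Follow-up Phase will begin once a patient discontinues study drug or completes the Treatment Phase". The last scheduled contact is the phone call 28 days after the end-of-treatment (EOT) visit, which serves as the end-of-study (EOS) visit. Section 4.4 defines completion: "A patient is considered to have completed the study when he/she has completed his/her last scheduled visit", or the last procedure in the schedule. It does not require six completed cycles.

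**The concern.** The rows of Table 14.1.1 are the drug-stopping reasons of protocol 7.1, but they sit under study discontinuation. A patient can stop acalabrutinib early, have the EOT assessment, take the EOS call and be recorded as having completed the study. That patient's reason for stopping drug then appears in no table, unless it was an adverse event. No planned table counts how many patients finished or stopped the six-cycle treatment.

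The stake is descriptive, because the trial tests no hypothesis. A reader of the report would take the disposition table as the tolerability result and may read study completion as six cycles taken. If sites classify differently, the total mixes two definitions. Under the literal reading, the better a site follows its stopped patients, the fewer discontinuations it shows.

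**Working it through.** **1. The plan's own figures.** Protocol Table 8 gives Clopper-Pearson 95% intervals. The lower limit is the 0.025 quantile of Beta(x, n−x+1) and the upper limit the 0.975 quantile of Beta(x+1, n−x). For x = 10, n = 100 this gives 4.90% to 17.62%, as printed. All 43 cells reproduce to two decimals. No stated figure is in dispute.

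**2. One patient traced through the text.** Take a patient whose disease progresses before Day 168.

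- Protocol 4.1.2: drug stops, the EOT evaluations are done, and the patient enters safety follow-up.
- Protocol 4.1.4: the call 28 days after EOT is the EOS visit, and sites are told to make every effort to conduct it.
- Protocol 4.4: with the last scheduled visit done, the patient has completed the study.
- SAP 5.3, Table 14.1.1, Listing 16.2.1.2: the patient counts as a completer, and progression is not counted as a reason.

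The last sentence of protocol 7.1 conflicts with this. It speaks of a patient discontinued from the study who is then followed until the next anti-cancer treatment or for up to 28 days. On that wording the same patient is a study discontinuation, with progression as the reason.

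**3. Do other outputs close the gap?**

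- Table 14.3.1 has a Drug Withdrawn row under action taken. It captures stops due to adverse events, but as a percentage of patients with any adverse event, not of the FAS.
- Listing 16.2.7.2 shows dispensing for Cycles 2 to 6. Listing 16.2.7.3 has a yes/no field for a change in dosing, with a comment. Neither gives a coded reason or feeds a summary.
- Stops for progression, patient decision, non-compliance, new anti-cancer therapy or pregnancy have no other table.

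**4. Size.** The documents give neither a stopping rate nor the share of stopped patients who would be recorded as completers. Let d be the patients who stop drug early and f the share of them recorded as completers. The reasons table shows d × (1 − f) patients and loses d × f. The figures below assume 100 patients enrolled and all dosed, so that the enrolled set equals the FAS.

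| d (assumed) | f (assumed) | shown = d(1−f) | shown, % (95% CI) |
|---|---|---|---|
| 10 | 0 | 10 | 10% (4.90–17.62) |
| 10 | 0.5 | 5 | 5% (1.64–11.28) |
| 10 | 1 | 0 | 0% (0.00–3.62) |
| 15 | 0 | 15 | 15% (8.65–23.53) |
| 15 | 0.8 | 15 × 0.2 = 3 | 3% (0.62–8.52) |
| 15 | 1 | 0 | 0% (0.00–3.62) |
| 20 | 0 | 20 | 20% (12.67–29.18) |
| 20 | 0.5 | 10 | 10% (4.90–17.62) |
| 20 | 0.9 | 2 | 2% (0.24–7.04) |

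The loss runs from nothing to every early stop. Any lost stops that were due to adverse events can still be counted from Table 14.3.1, so what disappears from all tables is the remainder of d × f.

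**The case against.** The strongest reply is that Table 14.1.1 is a treatment-discontinuation table with a loose heading. Its rows match the 7.1 reasons for stopping drug, and it has no row of its own for loss to follow-up or death. The closing sentence of 7.1 uses study discontinuation for patients who are still followed. If sites work that way, every early stop gets a reason and nothing is lost.

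This reply stands in part. It rules out a stronger reading that a reader might infer: that the protocol counts early stoppers who finish follow-up as completers, so the numerator is certainly too small. No passage says so outright. It is inferred from 4.4 with 4.1.2 to 4.1.4, and 7.1 contains contrary wording. A reader might also infer that stops for toxicity go uncounted, but Table 14.3.1 and Listing 16.2.11.2 record them.

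Patient-level traces of stopping are planned too, since protocol 6.4 requires dose discontinuations to be entered in the eCRF. The outcome also sits in a list of safety items without saying which discontinuation it means.

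The reply does not remove the ambiguity. Two sections of the protocol support different classifications of the same course, the SAP offers one field for both events, and nothing in either document tells a site which to use.

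**Conclusion.** The point holds in a limited form. A listed primary outcome has no analysis in SAP 6.3.1. The one table of reasons is tied to study discontinuation, while its categories are reasons for stopping drug. The count of early stops and their reasons may therefore be under-counted or may mix two definitions.

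The effect falls mainly on reasons other than adverse events. Adverse-event stops are tabulated, though not as an FAS incidence, and SAP 6.3 assigns the primary endpoints to the FAS.

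The size depends on an unknown stopping rate and on how the completion form is filled in. At an assumed 15 early stops in 100, the table could show anything from 15.0% down to 0%. Confidence is moderate, because the completion form and its instructions are not in the documents. This should be changed, but it does not show that any reported figure will be wrong.

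**What to change.** 1. State in SAP 6.1.1 and 6.3.1 that reasons for discontinuation means discontinuation of study treatment.
2. Split SAP 5.3, Table 14.1.1 and Listing 16.2.1.2 into two blocks:
   - **Study treatment:** completed (Cycle 6 Day 28) or discontinued, with the 7.1 reason, as n and % of the FAS by cohort and in total. The listing carries the last-dose date and reason.
   - **Study:** completed (EOS contact made) or left early, with study-exit reasons such as withdrawal of consent, loss to follow-up and death.
3. Reconcile the closing sentence of protocol 7.1 with 4.4, or add an eCRF completion instruction, so that sites record the two events in the same way.

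The cost is SAP wording, one table shell and one listing. If the eCRF has a single completion form, a field for the reason for stopping drug, and the last-dose date if it is not already held, would have to be added. Since protocol 6.4 already requires dose discontinuations to be recorded, little new data collection should be needed.

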##### 5.4 Demographic and Baseline Characteristics

Demographic and baseline characteristics will be summarized based on the Full Analysis Set.

Descriptive summaries will be provided for the demographic and baseline characteristics. Demographic characteristics and baseline characteristics such as Age, Gender, Height, Race, etc. will be summarized and tabulated for Full Analysis set.

All the continuous variables (i.e., age, height etc.) will be summarized by n, mean, standard deviation, minimum, median and maximum values. All the categorical variables will be summarized as counts and percentages.

Document Title:	Document ID:	BP04-01
Statistical Analysis Plan	Version Number:	3.1
	Effective Date:	25-Nov-2021

## 6. Efficacy Analysis Strategy

### 6.1 Efficacy Endpoints

#### 6.1.1 Primary Endpoint

- Adverse Events (AEs), Serious Adverse Events (SAEs), and AEs of Special Interest (AESI) including Arrhythmias (Atrial Fibrillation), Anaemia, Hypertension, Bleeding, Infections, Reasons for discontinuation and second primary malignancies

#### 6.1.2 Secondary Endpoint

- Objective response to treatment.
- Health related quality of life (EORTC QLQC30 Questionnaire)

### 6.2 Efficacy Hypothesis

Not Applicable

### 6.3 Statistical Methods for Efficacy Analysis

All primary and secondary efficacy endpoints will be summarized by Full Analysis Set.

Categorical data will be summarized using frequencies and percentages. Continuous data will be summarized with descriptive statistics, including mean, standard deviation, median, minimum, and maximum.

#### 6.3.1 Primary Endpoint Analysis

Primary Endpoint evaluations will include adverse event monitoring, physical examinations, ECG monitoring, clinical laboratory investigations (haematology and biochemistry), vital sign measurements, ECOG performance status and death as observed by the Investigator.

Adverse Events (AEs), Serious Adverse Events (SAEs), and AEs of Special Interest (AESI) will be summarized using frequencies and percentages.

Physical examination will be collected as per visit scheduled. Physical examination results (normal /abnormal) from scheduled visits will be summarized for each body system. A listing will be provided for the Normal/abnormal physical examination parameters.

A 12-lead electrocardiogram (ECG) will be performed as per visit scheduled. ECG results (normal, abnormal clinically insignificant, abnormal clinically significant) will be summarized as counts and percentage.

Laboratory investigations (haematology and biochemistry) data will be collected as per visit scheduled. Laboratory values will be presented using the International System of Units (SI units). Observed values will be summarized descriptively (n, mean, median, standard deviation, minimum, and maximum values). A listing will be provided which contains data for each laboratory parameter.

Document Title:	Document ID:	BP04-01
Statistical Analysis Plan	Version Number:	3.1
	Effective Date:	25-Nov-2021

Vital signs will be performed as per visit scheduled. Vital signs parameters include Systolic Blood Pressure, Diastolic Blood Pressure, Heart Rate, Respiratory rate and Temperature. Descriptive summaries (n, mean, median, standard deviation, minimum and maximum values) of observed values in each vital sign parameter at each assessment visit will be presented. A listing will be provided for all vital signs parameters assessments.

ECOG will be performed as per visit scheduled. ECOG performance status will be summarized as counts and percentage.

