Creatinine (creatinine clearance)
Urea or Blood Urea Nitrogen, depending on local practice
Gamma-glutamyl transferase
Magnesium
Haptoglobin
b2-microglobulin

Note: CMV serology, HIV (anti-HIV1 Ab, anti-HIV2 Ab), Hepatitis serology testing will be conducted at the screening that includes hepatitis B surface antigen (HBsAg), hepatitis B surface antibody (HBsAb), anti-HBc, and HCV antibody.

The local GLP certified laboratory will perform haematology and clinical chemistry tests. Additional analyses may be performed if clinically indicated.

Any clinically significant abnormal laboratory values should be repeated as clinically indicated and recorded in the eCRF.

All patients who have any Common Toxicity Criteria (CTC) Grade 3 or 4 laboratory values at the time of completion or discontinuation from study must have further tests performed until the laboratory values have returned to CTC Grade 1 or 2, unless these values are not likely to improve because of the underlying disease.

Urine Pregnancy Test

Urine pregnancy tests will be required only for women of childbearing potential. Urine pregnancy tests will be performed at Screening; on Cycle 1 Day 1; on Day 28 of Cycles 1-6; and at the early termination or End of study visit.

Physical examinations

For timing of individual measurements refer to the schedule outlined in (Table 1).

A complete physical examination will be performed and will include an assessment of the following (as clinically indicated): general appearance, respiratory, cardiovascular, abdomen, skin, head, neck (including ears, eyes, nose, and throat), lymph nodes, thyroid, musculoskeletal (including spine and extremities), and genital/rectal and neurological systems.

Symptom-directed physical exams, including tumour assessments by palpation, will be done during the treatment period and at the EOT visit.

Lymph nodes: The bi-dimensional diameters of the largest palpable lymph node/s in each of the following sites should be recorded: cervical, axillary, and inguinal. The dimensions of the liver and spleen below their respective costal margins, as assessed by palpation, should also be recorded.

Performance status will be assessed using ECOG performance status.

Vital signs

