The timings of assessments for vital signs are provided in Table 1 (SoA). Patients will be monitored with the assessment of vital signs (Blood Pressure, pulse, respiratory rate, and temperature) at screening and at each subsequent visit in the treatment phase. Additional monitoring with the assessment of vital signs is at the discretion of the Investigator per standard clinical practice or as clinically indicated. The date and time of collection and measurement will be recorded in the eCRF.

Electrocardiograms (ECG)

Resting 12-lead ECGs will be recorded at screening and as clinically indicated throughout the study. ECGs should be obtained after the patient has been rested in a supine position for at least 5 minutes and recorded while the patient remains in that position. In case of clinically significant ECG abnormalities, including a QTc value >480 ms, 2 additional 12-lead ECGs should be obtained over a brief period (e.g., 30 minutes) to confirm the finding.

All ECGs should be assessed by the Investigator for clinically significant abnormalities. If there is a clinically significant abnormal finding, the Investigator will record it as an AE on the eCRF.

At screening, the mean QTc with Bazett's correction ($QTcB = QT/\sqrt{R}$) must be <480 msec as per the eligibility criteria of the study.

Chest X-Ray

Patients with signs and symptoms of Pneumonia will be allowed to go for chest X-ray investigation. A symptom directed chest X-ray will be conducted at screening and all subsequent visits during the study duration.

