Appendix C Recommended Treatment Modifications for Acalabrutinib and Management Recommendations

Recommended dose modifications of Acalabrutinib for Grade ≥ 3 adverse reactions are provided in Table 9.

The administration of Acalabrutinib must be temporarily interrupted to manage a Grade ≥ 3 non-haematological treatment-related adverse reaction, Grade 3 thrombocytopenia with significant bleeding, Grade 4 thrombocytopenia, or Grade 4 neutropenia lasting longer than 07 days. Upon resolution of the adverse reaction to Grade 1 or baseline (recovery), administration of Acalabrutinib must be restarted as recommended in Table 9.

Table 9: Recommended Dose Adjustments for Adverse Reactions*

Adverse Reaction Occurrence	Dose Modification (Starting dose = 100 mg twice daily)
1 st and 2 nd	Restart at 100 mg twice daily
3 rd	Restart at 100 mg daily
4 th	Discontinue Acalabrutinib

*Adverse reactions graded by the National Cancer Institute Common Terminology Criteria for Adverse Events (NCI CTCAE) version 4.03.

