**Table 14.3.2. Summary of Physical examination**

	CLL/SLL (N=xx)	MCL (N=xx)	Total (N=xx)
	n (%)	n (%)	n (%)
Visit x			
Physical examination performed			
Yes	xx (xx.xx)	xx (xx.xx)	xx (xx.xx)
No	xx (xx.xx)	xx (xx.xx)	xx (xx.xx)
System x			
Normal	xx (xx.xx)	xx (xx.xx)	xx (xx.xx)
Abnormal NCS	xx (xx.xx)	xx (xx.xx)	xx (xx.xx)
Abnormal CS	xx (xx.xx)	xx (xx.xx)	xx (xx.xx)

- The Capital "N" in the column header represents the total number Full Analysis Set.
- The small "n" in summary statistics represents the total number of Patients.
- Percentages in the "Physical Examination performed" rows are based on number of patient in each group.
- Percentages in the "System x" rows are based on number of Patient Physical Examination performed in each group.
- Programmer Note: Generate summaries for the following System x :General Appearance, Skin, Eyes, Ears, Nose, Throat, Lungs, Heart, Abdomen, Extermities, Musculoskeletal System, Lymphatic System, Nervous System, Liver, Spleen and Other.
- NCS= Non-clinically significant
- CS= clinically significant
- Programme Note: Visit x- Visit 1 up to Visit 8
- Source :Listing 16.2.13

Document Title:	Document ID:	BP04-01
Statistical Analysis Plan	Version Number:	3.1
	Effective Date:	25-Nov-2021

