**Table 14.3.4.1. Summary of Laboratory assessment for Haematology**

	CLL/SLL (N=xx)	MCL (N=xx)	Total (N=xx)
Visit x			
Sample Collected			
Yes	xx (xx.xx)	xx (xx.xx)	xx (xx.xx)
No	xx (xx.xx)	xx (xx.xx)	xx (xx.xx)
Haematology Parameter x			
n	Xx	Xx	Xx
Missing	Xx	Xx	Xx
Mean (SD)	xx.x (xx.xx)	xx.x (xx.xx)	xx.x (xx.xx)
Median	xx.x	xx.x	xx.x
(min, max)	(xx.xx, xx.xx)	(xx.xx, xx.xx)	(xx.xx, xx.xx)

- The Capital "N" in the column header represents the total number Full Analysis Set.
- The small "n" in summary statistics represents the total number of Patients.
- SD = Standard Deviation, min=minimum, max=maximum
- Percentages in the "Sample collected" rows are based on number of patient in each group.
- Programmer Note: Generate summaries for the following Haematology parameters x: Haematocrit (%), Haemoglobin (g/dL), Neutrophils (%), Basophils (%), Eosinophils (%), Monocytes(%), Absolute Lymphocytes Count(thou/μL), Percentage Lymphocytes (%), Reticulocyte (%), Absolute Neutrophils Count (thou/μL), Platelet Count (thou/μL), Total leukocyte count(thou/μL).
- Programmer Note Visit x: Visit 1 up to Visit 8
- Source :Listing 16.2.15.1

Document Title:	Document ID:	BP04-01
Statistical Analysis Plan	Version Number:	3.1
	Effective Date:	25-Nov-2021

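### Asymptomatic, non-serious laboratory or vital-sign worsening that is sampled only between Visits 1 to 8 reaches no summary table, because the SAP has no rule for unscheduled and repeat results

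*SAP*

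**What the plan says.** **SAP.** Section 6.3.1 makes laboratory results, vital signs, ECGs and examinations part of the primary endpoint evaluations. On laboratory data it says "Laboratory investigations (haematology and biochemistry) data will be collected as per visit scheduled", which concerns collection rather than what enters a table. For vital signs it promises descriptive summaries "of observed values in each vital sign parameter at each assessment visit will be presented". Only for examinations does the text itself restrict the summary: "Physical examination results (normal /abnormal) from scheduled visits will be summarized for each body system".

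For laboratory data the restriction comes from the shells. The note to Table 14.3.4.1 reads "Programmer Note Visit x: Visit 1 up to Visit 8", and Tables 14.3.4.2 (biochemistry), 14.3.5 (vital signs), 14.3.3 (ECG) and 14.3.2 (examination: "Programme Note: Visit x- Visit 1 up to Visit 8") carry the same limit. Each laboratory and vital-sign block prints n, mean, SD, median, minimum and maximum for one visit. There is no block across all post-dose values, no visit window, and no rule for unscheduled or repeat results.

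**Protocol.** Section 8 allows repeat or unscheduled blood samples, for safety or because of technical problems. Section 8.1.2 allows additional safety samples and extra vital-sign monitoring, and says "Any clinically significant abnormal laboratory values should be repeated as clinically indicated and recorded in the eCRF". For a clinically significant ECG abnormality, "2 additional 12-lead ECGs should be obtained over a brief period (e.g., 30 minutes) to confirm the finding".

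Section 8.2.7 says mandated laboratory and vital-sign results will be summarised in the study report. For that reason it makes deterioration an AE only if it is serious or the reason for discontinuing treatment. If symptoms accompany it, the symptom is the AE.

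**The concern.** The rule in 8.2.7 works only if the summary it relies on contains the result. If a value exists solely between two scheduled visits, the by-visit tables have no row for it, and even the printed minimum and maximum leave it out.

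This matters because between-visit samples are taken selectively, often when something is suspected. Two of the named AEs of special interest, anaemia and hypertension, are closely tied to these data. The protocol itself depends on such samples: Appendix C names "Grade 4 neutropenia lasting longer than 07 days" among its triggers, and that duration cannot be established from visits 28 days apart.

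The gap is separate from the absence of change-from-baseline or shift tables. Either of those, built on Visits 1 to 8, would miss the same values.

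**Working it through.** The plan states no figure on this point. Its only computed statistical figures, the exact intervals in protocol Table 8, reproduce in all 43 cells and are not in question.

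**Step 1. Where a result found only between visits can go** (protocol 8.1.2 and 8.2.7, SAP shells).

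| Result | By-visit table | AE table 14.3.1 | Listing |
|---|---|---|---|
| Mandated laboratory value or vital sign, serious or reason for stopping | no | yes | possible |
| Same, with symptoms | no | yes, as the symptom | possible |
| Same, asymptomatic, non-serious, treatment not stopped | no | **no** | possible |
| Clinically relevant worsening in a non-mandated parameter, asymptomatic | no | yes | possible |
| Clinically significant ECG finding, including QTc >480 ms | no | yes | possible |
| New or aggravated clinically relevant examination finding | no | yes, unless unequivocally due to the disease | possible |

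Only the third row is absent from every summary. For QTcB the finding is counted as an AE, and only the measured value is missing from Table 14.3.3.

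**Step 2. How often an episode falls wholly between visits (illustration).** Inputs from the Schedule of Activities: Visits 2 to 7 on Day 1 of each 28-day cycle, and the end-of-treatment visit on Day 170. The visit days are 1, 29, 57, 85, 113, 141 and 170, with five gaps of 28 days and one of 29.

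Assumption: onset is equally likely on each of Days 2 to 170, which is 169 days. An episode of d days (d up to 28) is present at one of the six later visits for 6d of those onset days.

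| d | Present at a visit | Wholly between visits |
|---|---|---|
| 7 | 42/169 = 24.9% | 127/169 = 75.1% |
| 14 | 84/169 = 49.7% | 85/169 = 50.3% |
| 21 | 126/169 = 74.6% | 43/169 = 25.4% |

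The shortcut 1 − d/28 gives 75%, 50% and 25%.

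**Step 3. How much of that is a loss of data.** An episode that nobody sampled is lost whatever the SAP says. Let s be the share of between-visit episodes that are sampled. The share of all episodes measured yet missing from the tables is (1 − d/28) × s. The documents give no sampling frequency, so s is shown over its range.

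| d | s = 0 | s = 0.25 | s = 0.5 | s = 1 |
|---|---|---|---|---|
| 7 | 0% | 18.75% | 37.5% | 75% |
| 14 | 0% | 12.5% | 25% | 50% |
| 21 | 0% | 6.25% | 12.5% | 25% |

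In patients: if 10 of 100 had one 7-day episode, 10 × 7/28 = 2.5 would be expected to contribute a value at a visit. Of the other 7.5, between none (s = 0) and all (s = 1) would have a recorded value that no table uses.

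**The case against.** A reader might infer that unscheduled results of every kind never reach a safety summary. The documents do not support that. Protocol 8.1.2 counts QTc >480 ms among clinically significant ECG abnormalities and has such findings recorded as AEs. Section 8.2.7 does the same for new examination findings, and it keeps serious, symptomatic or treatment-ending laboratory and vital-sign changes in the AE data. All of these are counted in Table 14.3.1, though without event terms or measured values. For a patient who stops early, protocol 4.1.3 treats the last visit as the end-of-treatment visit, so those values do have a column.

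A second tempting inference is that leaving out repeats pulls the extremes towards normal. Where the triggering value came from a scheduled visit, it is already in that visit's minimum or maximum, and the repeat adds nothing to the extreme. The bias argument applies only to values first found between visits.

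Other points also stand:
- Except for examinations, the SAP is silent on unscheduled data rather than excluding them.
- The laboratory and vital-sign listings have a visit column and no limit to Visits 1 to 8, so they can show the values. In a descriptive study of about 100 patients that is real disclosure, but it is not a summary.
- Appendix B 1 names an abnormal laboratory finding as a possible AE, so some sites may log one anyway. Section 8.2.7 is the more specific rule and says otherwise.
- A dose interruption would appear in Listing 16.2.7.3, but Table 14.3.1 has no interruption row under action taken.

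None of this gives the third row of Step 1 a place in a summary.

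**Conclusion.** The point holds for laboratory and vital-sign results that are asymptomatic, non-serious, not a reason for stopping treatment, and measured only between scheduled visits. Followed as written, the plan leaves them in listings at most. It does not hold in the same way for ECG and examination findings.

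The size is uncertain. The 75% (7 days) and 50% (14 days) describe episodes that miss a visit. They rest on uniform onset and a fixed 28-day grid, and they cap the loss rather than measure it. It would be wrong to read them as the share of abnormalities the trial will fail to report. With no between-visit sampling the loss attributable to the SAP is nil.

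No stated figure is wrong and no conclusion is overturned. The change is still worth making, because these data belong to the primary endpoint evaluations and the values are already collected.

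**What to change.** Keep the by-visit blocks as they are. Add to Tables 14.3.4.1, 14.3.4.2 and 14.3.5, and for QTcB in Table 14.3.3, one block titled *Worst value after first dose, all assessments*. It takes one value per patient from scheduled, unscheduled and repeat results. Define the direction for each parameter, and show both the lowest and the highest value where either is abnormal, for example potassium, sodium, calcium and glucose.

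State in SAP 6.3.1 that:
- unscheduled and repeat results enter this block and not the by-visit means;
- a repeat taken because of a technical problem with the sample replaces the faulty value.

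Table 14.3.2 needs no such block, since new clinically relevant examination findings are recorded as AEs.

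The cost is a short rule in 6.3.1, one block per shell and some programming; no new data are needed. There is one downside, to be footnoted: patients sampled more often have more chances of an extreme value. The block also does not count how many patients worsened by grade, which would be a separate addition.
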